5.1.3 Subject Exclusion Criteria

The subject must be excluded from participating in the trial if the subject:

1. Has bilateral sacroiliitis Grade 2 or unilateral sacroiliitis Grade 3 or Grade 4 on conventional x-rays (to exclude subjects who meet modified New York criteria for AS).
Note: SI-joint x-rays must undergo central reading to determine study eligibility. Subjects who have a SI joint x-ray performed within 6 months prior to Screening do not need to have a SI joint x-ray repeated at Screening.
2. If female, is nursing, pregnant, or intending to become pregnant within 6 months after receiving the last administration of trial medication.
3. Intends to donate eggs (female subjects) or sperm (male subjects) while receiving trial medication or within 6 months after the last dose of trial medication.
4. Has any clinically significant condition or situation, other than those listed as exclusion criteria that, in the opinion of the investigator, would interfere with the trial evaluations or participation in the trial.
5. Has ever received any cytotoxic drugs, including but not limited to chlorambucil, cyclophosphamide, nitrogen mustard, or other alkylating agents.

6. Has received any treatment listed in the table below more recently than the indicated off-drug period prior to Screening.

Medications, Supplements, and Other Substances that are Prohibited for Trial Entry

Prohibited Medications, Supplements, and Other Substances	Off-Drug Period Prior to Screening
Disease modifying anti-rheumatic drugs such as but not limited to: Methotrexate Sulfasalazine Leflunomide Hydroxychloroquine Steroids (oral, parenteral, intra-articular) Cyclosporine (Note: ophthalmic use is allowed) Mycophenolate mofetil Azathioprine.	30 days (8 weeks for leflunomide unless subject undergoes standard cholestyramine or activated charcoal washout)
Live vaccinations	3 months
Investigational medications	30 days or 5 half lives (whichever is longer)
Bacille Calmette-Guerin (BCG) vaccination	12 months

7. Has ever received TNF- α targeted therapy or any other biological agents intended to treat immune-mediated diseases, including but not limited to infliximab, etanercept, adalimumab, certolizumab, golimumab, alefacept, efalizumab, rituximab, natalizumab, secukinumab, ixekizumab, ustekinumab, or vedolizumab.
8. Has an allergy/sensitivity to golimumab or its excipients.
9. Has any systemic inflammatory condition from Screening up to Baseline with signs and symptoms including, but not limited to:
- a. psoriatic arthritis,
 - b. active Lyme disease,
 - c. systemic lupus erythematosus,
 - d. infectious arthritis,
 - e. vasculitis,
 - f. parvovirus infection,
 - g. rheumatoid arthritis,
 - h. active uveitis,
 - i. active IBD.
10. Has a history of latent or active granulomatous infection, including histoplasmosis, or coccidioidomycosis, prior to Screening.
11. Had a nontuberculous mycobacterial infection or opportunistic infection (e.g., cytomegalovirus, Pneumocystis jirovecii [carinii], aspergillus) within 6 months prior to Screening.
12. Has a history of an infected joint prosthesis, or has received antibiotics for a suspected infection of a joint prosthesis, if that prosthesis has not been removed or replaced.

13. Had a serious infection (including but not limited to, hepatitis, pneumonia, sepsis, or pyelonephritis), or has been hospitalized for an infection, or has been treated with IV antibiotics for an infection within 2 months prior to Baseline. Less serious infections (eg, acute upper respiratory tract infection, simple urinary tract infection) need not be considered exclusionary at the discretion of the investigator.
14. Had a history of, or ongoing, chronic or recurrent infectious disease, including but not limited to, chronic renal infection, chronic chest infection (e.g., bronchiectasis), sinusitis, recurrent urinary tract infection (e.g., recurrent pyelonephritis, chronic nonremitting cystitis), an open, draining, or infected skin wound, or an ulcer.
15. Is known to be infected with human immunodeficiency virus (HIV) or seropositive for hepatitis C virus (HCV).
Note: Subject infected with HCV is eligible if there are 2 negative HCV RNA test results 6 months apart prior to Screening and there is a third negative HCV RNA test result at Screening.
16. Has a chest x-ray within 2 months prior to Screening that shows an abnormality suggestive of a current active infection or malignancy.
17. Has a history of lymphoproliferative disease, including lymphoma, or signs suggestive of possible lymphoproliferative disease such as lymphadenopathy of unusual size or location and/or clinically significant splenomegaly, or monoclonal gammopathy of undetermined significance.
18. Has had a malignancy within 5 years before screening (exceptions are squamous and basal cell carcinomas of the skin that have been treated, with no evidence of recurrence for at least 3 months prior to Baseline; and carcinoma in situ of cervix that has been surgically cured).
19. Has a history of known demyelinating diseases such as multiple sclerosis or optic neuritis.
20. Has a history of or concurrent congestive heart failure ([CHF] of any grade [I-IV]), including medically controlled, asymptomatic CHF.
21. Has a transplanted organ (with the exception of a corneal transplant performed ≥ 3 months prior to baseline).
22. Has current signs or symptoms of severe, progressive, or uncontrolled renal, hepatic, cardiovascular, metabolic, ophthalmological, respiratory, hematologic, gastrointestinal, endocrine, pulmonary, neurologic, psychiatric, cerebral, or other significant medical illness or disorder that, in the judgment of the investigator, could interfere with the trial, or require treatment that might interfere with the trial. Other conditions that are well controlled and stable will not prohibit participation if deemed appropriate per the investigator's judgment. The Sponsor's medical monitor should be consulted if there are any questions regarding a specific medical condition.
23. Is a user of recreational or illicit drugs or has or had a substance abuse (drug or alcohol) problem within the previous 2 years.

24. Has participated in any other interventional clinical trial within 30 days, inclusive, of signing the informed consent form of the current trial.
25. Is or has an immediate family member (e.g., spouse, parent/legal guardian, sibling or child) who is investigational site or sponsor staff directly involved with this trial.

5.2 Trial Treatment(s)

The treatments to be used in this trial are outlined below in [Table 1](#).

Table 1 Trial Treatment

Biologic	Dose/Potency	Dose Frequency	Route of Administration	Regimen (Treatment Period)	Use
Golimumab	Per approved label: 50 mg (or 100 mg)†	Every month (QM)	Subcutaneous (SC)	Open-label from Month 0 to Month 9 (Period 1); switch to open-label golimumab upon “flare” (Period 2)	Standard of Care
Golimumab (full-treatment regimen)	Per approved label: 50 mg (or 100 mg)†	Every month (QM)	Subcutaneous (SC)	Double-blind monthly injections of active golimumab for 12 months (or until “flare”)	Experimental
Golimumab (reduced-treatment regimen)	50 mg (or 100 mg)†	Every 2 months (Q2M)	Subcutaneous (SC)	Double-blind monthly injections of active golimumab, alternating with placebo for golimumab, for 12 months (or until “flare”)	Experimental
Matching placebo for golimumab		Every month (QM)	Subcutaneous (SC)	Double-blind monthly injections of placebo for golimumab for 12 months (or until “flare”)	Experimental
† For subjects with body weight more than 100 kg, increasing the dose of golimumab to 100 mg may be considered during the Open-label Period 1 (and would continue during Period 2, depending on the randomization schedule).					

The frequency of SC injections is monthly during the entire trial. After an initial dose has been given, administration then continues preferably on the same day of every month (consistent with approved labeling) with an allowed window of ± 5 days. As the trial progresses, the day of the month that is targeted for dosing can be re-set, if needed (see Section 7.1.1.10). Depending on the period of the trial (open-label Period 1 or double-blind Period 2) and on the randomization schedule for treatment withdrawal or continued treatment (during Period 2), an individual injection may contain active golimumab or a matching placebo.

The first dose of golimumab 50 mg SC is administered at the study center by site personnel on the day of enrollment at Visit 2 (considered “Month 0”). If allowed by local guidelines and after proper training in injection technique, subjects may self-inject if determined by their physician that it is appropriate and with medical follow-up as necessary. For subjects with a body weight of more than 100 kg, increasing the dose of golimumab to 100 mg SC may be considered; see Section 5.2.1.2.

Open-label golimumab is administered monthly during Period 1. After 10 months on open-label therapy, eligible subjects will be randomized, in a double-blind manner, to 1 of 3 treatment arms to receive either matching-placebo for golimumab (i.e., treatment withdrawal), continued treatment with golimumab every month (as a full-treatment regimen), or continued treatment with golimumab every 2 months (as a reduced-treatment regimen), via monthly injections that alternate between golimumab and matching placebo. If a “flare” is confirmed, subjects are treated with open-label golimumab monthly until Month 22 (end of Period 2). There should be an interval of at least 10 days between the last dose of Period-2 assigned double-blind therapy and starting open-label golimumab.

All supplies indicated in [Table 1](#) above will be provided centrally by the Sponsor or locally by the trial site, subsidiary or designee, depending on local country operational or regulatory requirements.

For any commercially available product that is provided by the trial site, subsidiary or designee every attempt will be made to source these supplies from a single lot/batch number. The trial site will be responsible for recording the lot number, manufacturer and expiry date of any locally purchased product.

The investigator shall take responsibility for and shall take all steps to maintain appropriate records and ensure appropriate supply, storage, handling, distribution and usage of trial treatments in accordance with the protocol and any applicable laws and regulations.

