If a “flare” occurs during Period 2, then subjects discontinue blinded therapy (placebo, golimumab QM, or golimumab Q2M) and begin re-treatment with open-label golimumab QM. There should be an interval of at least 10 days between the last dose of Period-2 double-blind therapy and the first dose of open-label golimumab after a “flare” is confirmed. Thereafter, it is expected that re-treatment with open-label golimumab continues monthly through the end of Period 2. A clinical response to re-treatment is defined as a BASDAI score improvement of ≥ 2 or $\geq 50\%$ improvement (measured relative to the mean of the 2 BASDAI scores that were collected at the 2 consecutive assessments that defined the “flare”) that occurs within 3 months of restarting open-label treatment. If a subject shows insufficient improvement after 3 months of restarting open-label treatment for a “flare”, the investigator may consider discontinuing this subject from the study (based on clinical judgment) and will ensure a safety follow-up telephone call 3 months after the last dose of trial medication. If the subject is determined to have experienced a first “flare” between Months 19 and 22, the subject then completes a course of re-treatment (i.e., 3 monthly open-label golimumab injections) and will have a safety follow-up telephone call 3 months after the last dose of open-label golimumab. Subjects who do not experience a “flare” during Period 2 are to complete the study at Month 22 and will have a safety follow-up telephone call 3 months after their last dose of blinded trial medication.

Approximately 300 subjects are expected to enter Period 1. Based on the response to golimumab observed in the recently completed GO-AHEAD trial (P07642) [1], approximately 114 subjects are expected to continue into Period 2, based on attaining inactive disease status (ASDAS < 1.3) at both Months 7 and 10 of open-label golimumab. If the number of subjects who attain inactive disease is fewer than expected, additional subjects may need to enter Period 1 in order to randomize approximately 114 subjects with inactive disease status in Period 2.

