It is anticipated that most of the subjects who enter Period 2 will participate in the trial for up to approximately 27 months from the time the subject signs the ICF through the final contact. For subjects determined to have experienced a “flare” for the first time between Months 19 and 22, the duration of participation in the trial may exceed 27 months (i.e., up to 30 months) to allow completion of a 3-month course of re-treatment after the “flare”.

Specific procedures to be performed during the trial, as well as their prescribed times and associated visit windows, are outlined in the Trial Flow Chart - Section 6.0. Details of each procedure are provided in Section 7.0 – Trial Procedures.

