- b. Remote completion of the BASDAI questionnaire by subjects, twice monthly, using an electronic device.
- c. If the subject discontinued from the trial during Period 2, trial medication will not be administered at the DC clinic visit.
- d. If subjects report an increase of ≥ 2 BASDAI score compared with Month 10 (Visit 23), site is to call subject to obtain Patient Global Disease Assessment, and then use the CRP value from the previous clinic visit to calculate ASDAS. See Section 7.1.5.4 for more details.
- e. If “flare” (defined as ASDAS absolute score ≥ 2.1 and/or post-withdrawal increase (i.e., change from Visit 23) of ≥ 1.1 at 2 consecutive visits) is confirmed *during* a “flare confirmation” visit (based on the BASDAI and PGD_N obtained at that visit), subject will begin re-treatment with open-label golimumab for the confirmed “flare” at that visit. Clinic visits are then to be scheduled every 2 months from the date of the initial re-treatment with open-label golimumab
- f. If “flare” is confirmed *after* a “flare confirmation” visit (based on the CRP result as eventually received from that visit), then the subject is asked to return to the clinic to begin re-treatment with open-label golimumab for the “flare”. Clinic visits are then to be scheduled every 2 months from the initial re-treatment with open-label golimumab.
- g. The safety follow-up phone call is made approximately 3 months after the last dose of trial medication.
- h. When it is confirmed at Visit 23 that a subject is eligible for Period 2, site to call IVRS/IWRS to randomize the subject into Period 2 (Double-blind) prior to administering the trial medication; assign trial medication at all clinic visits; update the subject status at V48/DC visit.
- i. During Period 2, site personnel will administer the trial medication (± 5 days) during clinic visits. If subjects are self-injecting, the monthly dose to be administered (± 5 days) between clinic visits will be dispensed for subjects to self-inject at home.
- j. PEs would include a full skin assessment and would be directed to evaluate signs and symptoms of potential AEs assessment.
- k. If local law requires more frequent pregnancy testing, the site will perform the assessments as per local requirement
- l. At all visits, samples MUST be collected BEFORE the administration of trial medication.
- m. The same sample will be used for detection of antibodies to golimumab and neutralizing antibody analysis.

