7.1.2.6 Bath Ankylosing Spondylitis Disease Activity Index (Patient Reported Outcome)

Subjects will complete the BASDAI by answering 6 questions at all clinic visits, as well as twice monthly between clinic visits, using the 0 to 10 NRS. Subjects will be instructed by site personnel on how to use an electronic device to record their ratings for each question; subjects will also be able to use an electronic device remotely (i.e., at home) to record their ratings between clinic visits.

Q1. Fatigue/tiredness	Over past week: 0 to 10 = None to Very severe
Q2. Neck, back, or hip (spinal) pain	Over past week: 0 to 10 = None to Very severe
Q3. Pain/swelling in joints other than neck, back, or hip	Over past week: 0 to 10 = None to Very severe
Q4. Tenderness	Over past week: 0 to 10 = None to Very severe
Q5. Level of morning stiffness	Since awakening: 0 to 10 = None to Very severe
Q6. Duration of morning stiffness	Since awakening: 0 to 10 = Zero to 2-or-more hours

Calculation of the BASDAI score is described in Section 8.4.3. Three of the questions on the BASDAI are also components of the ASDAS, as described in Section 8.4.3. Details on scales and questions are provided in Appendix 12.6 [9].

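### Sections 5.2 and 7.1.5.5 stop re-treatment at Month 22, contrary to the Section 2.1 exception for late flares, and no BASDAI is explicitly scheduled for the end of a late response window

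*Combined protocol and SAP*

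**What the plan says.** **Dosing after a flare.** Section 2.1 gives a general rule: "it is expected that re-treatment with open-label golimumab continues monthly through the end of Period 2". It then makes an exception for a first flare between Months 19 and 22, where "the subject then completes a course of re-treatment (i.e., 3 monthly open-label golimumab injections"). For these subjects participation "may exceed 27 months (i.e., up to 30 months) to allow completion of a 3-month course of re-treatment". Section 5.2 states only that "subjects are treated with open-label golimumab monthly until Month 22 (end of Period 2"). Section 7.1.5.5, decisions (1) and (2a), likewise ends monthly re-treatment with Period 2. Neither section repeats the exception or refers to it.

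**Response window.** Section 2.1 defines response to re-treatment as a BASDAI improvement "that occurs within 3 months of restarting open-label treatment". Response after re-treatment is the first-listed secondary endpoint in Section 8.4.1.2.

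**BASDAI schedule.** In the Section 6.2 flow chart the last remote BASDAI column is Month 21.5 and the last numbered visit is Visit 48 at Month 22. After that there is only the safety call, without BASDAI. Footnote e adds, for re-treated subjects: "Clinic visits are then to be scheduled every 2 months from the date of the initial re-treatment with open-label golimumab". Footnote f says the same for flares confirmed later by CRP. Section 7.1.2.6 adds: "Subjects will complete the BASDAI by answering 6 questions at all clinic visits, as well as twice monthly between clinic visits".

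**The concern.** Sections 5.2 and 7.1.5.5 are where a site looks to decide how many injections to give and when to stop. For a late flare they give a different answer from Section 2.1, so the course a subject receives could depend on which section the site reads.

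The second problem is measurement. BASDAI alone determines response to re-treatment. If it is not collected to the end of the window, a response in the last weeks cannot be seen. The exploratory extent of response in Section 8.4.1.3 names 12 weeks after re-treatment, which falls in that stretch. So does the investigator's decision, in Section 2.1, on insufficient improvement after 3 months.

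There is also an edge case. A flare first seen at Visit 48 can be confirmed up to 3 weeks later, after Month 22. The documents do not say whether the exception covers it, or whether it counts as a flare during Period 2 for the flare FAS in Section 8.5.1.

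**Working it through.** **1. The plan's own durations.** Standard participation: 2 (screening) + 10 + 12 + 3 (safety call) = 27 months. With a 3-month late course: 27 + 3 = 30. Bottom-up for the latest case: confirmation 3 weeks after Month 22 is about Month 22.7. Then 2 + 22.7 + 2 (to the third injection) + 3 (to the call) = 29.7 months. The 30-month limit fits the exception, including a flare confirmed just after Visit 48.

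**2. Injections under the literal 5.2 and 7.1.5.5 text.** For a restart at month *r*, doses fall at *r*, *r*+1, *r*+2 and so on; the ±5-day dosing window is ignored.

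| Restart *r* | Injections by Month 22 | Section 2.1 course |
|---|---|---|
| Month 20 | 3 | 3 |
| after 20, to 21 | 2 | 3 |
| after 21, to 22 | 1 | 3 |
| after 22 (flare confirmed after Visit 48) | 0 | not stated |

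The course is cut only for restarts after Month 20.

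**3. BASDAI coverage.** The window ends at *r*+3.
- Numbered columns of 6.2 alone: coverage ends at Month 22, so the window is incomplete for any restart after Month 19, by *r*+3−22 months.
- With footnotes e/f and Section 7.1.2.6: BASDAI is implied up to the visit at *r*+2 (Month 23 for a Month 21 restart, Month 24 for a Month 22 restart). For restarts after Month 20 the gap is then from *r*+2 to *r*+3. Since the third injection is due at *r*+2, no BASDAI is explicitly scheduled after it. A 4-month visit, if held, would bring in questionnaires between, but nothing says it is held.

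**4. How many flares.** Inputs from Sections 8.1 and 8.9: 38 per arm; flare-free at 12 months 30% on placebo. The Q2M rate is stated there to be unknown; I take 80% to 60%. Further assumptions: flare date equals restart date, and S(t) = S(12)^((t/12)^k), with t in months since Month 10. k = 1 is a constant hazard; the range uses k = 0.75 to 1.5.

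Total placebo plus Q2M flares: 38 × 0.70 + 38 × 0.20 = 34.2, up to 38 × 0.70 + 38 × 0.40 = 41.8.

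Expected late flares per arm = 38 × (S(a) − S(12)). For a = 9 and k = 1: placebo 38 × (0.4054 − 0.30) = 4.00; Q2M 38 × (0.8459 − 0.80) = 1.74, or 38 × (0.6817 − 0.60) = 3.11.

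| Restart | Flares, k = 1 | Share, k = 1 | Share, k = 0.75 to 1.5 | What is at risk |
|---|---|---|---|---|
| after Month 19 (a = 9) | 5.7-7.1 | 17% | 13-25% | end of response window |
| after Month 20 (a = 10) | 3.7-4.6 | 11% | 8-16% | at least one injection |
| after Month 21 (a = 11) | 1.8-2.2 | 5% | 4-8% | two injections |
| last half month (a = 11.5) | 0.9-1.1 | 3% | 2-4% | possible confirmation after Visit 48 |

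**5. Questionnaires added by the fix.** Twice monthly after Month 22 until *r*+3 gives 2 × (*r* − 19) per subject: 2 at *r* = 20, 6 at *r* = 22, about 7 at *r* = 22.7. The expected number per arm is 38 × ∫ 2(t − 9) f(t) dt over t = 9 to 12, where f is the flare density; this equals 76 × [∫ S(t) dt − 3 S(12)]. For k = 1: placebo 76 × (1.0502 − 0.90) = 11.4; Q2M 5.2 (80%) to 9.1 (60%). Placebo plus Q2M: 16.6-20.5. Adding QM at 80% (5.2): 21.8-25.7, or 16.5-38.0 across hazard shapes. These counts do not subtract questionnaires already implied by footnotes e/f.

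**The case against.** **The design intent is not in doubt.** Section 2.1 states rule and exception together and extends participation for this purpose, and Table 1 in Section 5.2 sets no Month 22 stop on re-treatment. This stands: it is a failure to harmonise sections, not a missing rule. A site that follows 2.1 gives the full course.

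**A reader might infer that no BASDAI is collected after Month 22.** That is true only of the numbered columns. Footnotes e/f and Section 7.1.2.6 put a BASDAI inside the window even for a Month 22 restart. What remains is the stretch between the 2-month visit and month 3.

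**A reader might infer that late flares will be scored as non-responders and bias the estimate downward.** The documents support this only in part. Section 8.6.1 assigns non-response to subjects who are not re-treated or who discontinue. A subject given one or two injections and followed to Month 22 was re-treated and completed the period, so neither rule clearly applies. The route is documented only for a flare confirmed after Visit 48 that literal 5.2 leaves untreated, if that flare is counted at all. Also, a response at any point in the window counts, so an unmeasured last month loses only later responders.

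**The counts may be high.** The 17% includes restarts in Months 19-20, which receive all three injections even under literal 5.2. Section 8.6.1 counts discontinuation before a flare as a flare, so re-treated subjects may be fewer than 34-42. Both points stand, and the figures are shares at risk, not shares lost.

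**The consequence is small.** Section 8.1 names no key secondary endpoints, and Section 8.8 makes everything beyond the primary comparisons supportive or exploratory. This also stands.

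**Conclusion.** The point holds and is minor. Sections 5.2 and 7.1.5.5 contradict the Section 2.1 exception. Followed literally, they shorten about 3.7-4.6 courses (11% of placebo plus Q2M flares; 8-16% across hazard shapes). For about 5.7-7.1 restarts after Month 19 (17%; 13-25%), the end of the response window has no explicitly scheduled BASDAI, although some of these subjects will already have responded. The sizes rest on 38 per arm, 30% flare-free on placebo, an assumed 60-80% on Q2M, restart on the flare date, and the assumed hazard shapes.

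The affected results are the re-treatment response proportion, reported with a Clopper-Pearson interval, and the exploratory time to and extent of response. A reader might extend the concern to the primary comparison. That does not follow: the primary endpoint is whether a flare occurs, which is settled before re-treatment starts, so its test and power are unchanged.

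**What to change.** 1. Carry the Months 19-22 exception (three monthly open-label injections) into Section 5.2 and into decisions (1) and (2a) of Section 7.1.5.5. State that it covers a flare first seen at Visit 48 and confirmed within the 3-week limit, and whether that flare belongs to the flare FAS.
2. Add a footnote to the Section 6.2 flow chart continuing the existing twice-monthly remote BASDAI until 3 months after the first open-label dose. This is needed for placebo and Q2M subjects; QM is optional because that arm is outside the flare FAS.

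Any window still incomplete can follow the Section 8.6.1 non-response convention, with a sensitivity analysis.

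**Cost.** Wording, plus about 17-21 remote questionnaires in total for placebo and Q2M, or 22-26 with QM (16-38 across hazard shapes), on a device already in use. Per subject this is at most six for a restart by Month 22, or about seven for a flare confirmed 3 weeks after Visit 48. No drug is needed beyond what Section 2.1 already provides, except for about one flare confirmed just after Visit 48.
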